6.4 Pregnancy

If, following initiation of the IP, it is subsequently discovered that a study subject is pregnant or may have been pregnant at the time of study exposure, including during at least 5 half-lives after product administration, the Investigator must immediately notify the BMS Medical Monitor/designee of this event and complete and forward a Pregnancy Surveillance Form to BMS Designee within 24 hours and in accordance with SAE reporting procedures described in [Section 6.1.1](#).

In most cases, the study drug will be permanently discontinued in an appropriate manner (eg, dose tapering if necessary for subject safety).

In the rare event that the benefit of continuing study drug is thought to outweigh the risk, after consultation with BMS, the pregnant subject may continue study drug after a thorough discussion of benefits and risk with the subject.

Protocol-required procedures for study discontinuation and follow-up must be performed on the subject unless contraindicated by pregnancy (eg, X-ray studies). Other appropriate pregnancy follow-up procedures should be considered if indicated.

The Investigator must immediately notify the BMS (or designee) Medical Monitor of this event and complete and forward a Pregnancy Surveillance Form to BMS (or designee) within 24 hours and in accordance with SAE reporting procedures described in [Section 6.1.1](#).

Follow-up information regarding the course of the pregnancy, including perinatal and neonatal outcome and, where applicable, offspring information, must be reported on the Pregnancy Surveillance Form.

Any pregnancy that occurs in a female partner of a male study participant should be reported to BMS. Information on this pregnancy will be collected on the Pregnancy Surveillance Form.

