Adequate monitoring and safety assessments as outlined in [Section 5.3](#) of the study protocol is in place for mitigating the risk of cytokine release should it occur at any point in the trial. A specific study of cytokine release potential in pre-clinical models for the combination is at this time unnecessary given the clinical safety profile.

Overall Risk/Benefit for Combination with Nivolumab

Nivolumab has demonstrated clinical activity in subjects with advanced NSCLC, RCC, melanoma and lymphomas among other tumors and has been recently approved in the treatment of second line melanoma following Yervoy and BRAF inhibitors for BRAFV600 mutant positive tumors, and second line squamous NSCLC.¹²¹

Nivolumab has demonstrated a manageable safety profile. The overall safety experience with nivolumab, as a monotherapy or in combination with other therapeutics, is based on experience in approximately 8,700 subjects treated to date.⁹⁷ There is no pattern in the incidence, severity, or causality of AEs to nivolumab dose level. The most common AEs included fatigue, rash, pruritus, diarrhea, and nausea. Side effects of nivolumab therapy may include those associated with immune-mediated activation, such as pneumonitis, thyroiditis, and transaminitis. Most of these events resolved with immunomodulating medication (e.g. < 1% subjects who developed pneumonitis (5/691) treated subjects have died.¹²¹ To mitigate risk from serious immune-mediated AEs, subject management algorithms for nivolumab-related AEs from prior collective nivolumab experience have been included ([Appendix 4](#)). For nivolumab monotherapy, the safety profile is similar across tumor types. The only exception is pulmonary inflammation AE), which may be numerically greater in subjects with NSCLC, because in some cases, it can be difficult to distinguish between nivolumab-related and unrelated causes of pulmonary symptoms and radiographic changes. The nonclinical findings of increased late-stage pregnancy loss and early infant deaths/euthanasia in nivolumab-exposed pregnant monkeys [REDACTED] suggest a potential risk to human pregnancy if there is continued treatment with nivolumab during pregnancy. However, nivolumab exposure during human pregnancy has not been permitted in clinical trials, and is not permitted in this protocol.

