3.11 Discontinuation of Subjects Following Any Treatment with Study Drug

Subjects MUST discontinue investigational product (IP) (and non-IP at the discretion of the Investigator) for any of the following reasons:

- Subject's request to stop study treatment and/or participation in the study
- Any clinical AE, laboratory abnormality or intercurrent illness which, in the opinion of the Investigator, indicates that continued participation in the study is not in the best interest of the subject
- Termination of the study by BMS
- Loss of ability to freely provide consent through imprisonment or involuntarily incarceration for treatment of either a psychiatric or physical (e.g., infectious disease) illness
- Pregnancy

- Documented and confirmed disease progression as defined by RECIST (see [Appendix 3](#)) unless subject meets criteria for treatment beyond progression (Section 3.11.1)
- Clinical deterioration while receiving active study therapy that in the opinion of the Investigator indicates that continued participation in the study is not in the best interest of the subject
- Discretion of the Investigator
- Inability to comply with the protocol requirements
- Protocol defined reasons for discontinuation (see [Section 4.3.6](#)).

In the case of pregnancy, the Investigator must immediately notify the BMS Medical Monitor/Designee of this event. In most cases, the study drug will be permanently discontinued in an appropriate manner. If the Investigator determines a possible favorable benefit/risk ratio that warrants continuation of study drug, a discussion between the Investigator and the BMS Medical Monitor/Designee must occur.

All subjects who discontinue IP should comply with protocol specified follow-up procedures as outlined in [Section 3.3](#). The only exception to this requirement is when a subject withdraws consent for all study procedures including post-treatment study follow-up or loses the ability to consent freely (e.g., is imprisoned or involuntarily incarcerated for the treatment of either a psychiatric or physical illness).

If study drug is discontinued prior to the subject's completion of the study, the reason for the discontinuation must be documented in the subject's medical records and entered on the appropriate CRF page.

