4 TREATMENTS

All protocol-specified investigational and non-IPs are considered study drug:

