Thyroid function tests*	X	X	X	X		X	To include TSH with reflex testing (free T3 and free T4) if applicable. Results should be examined by the Investigator or appropriate designee within 48 hours of dose administration.

Table 5.1-2: On-Treatment Procedural Outline

Procedure	Cycles 1 -13					EOT ^{a,b}	Notes
	Day 1 (± 2 days)	Day 15 (± 2 days)	Day 29 (± 2 days)	Day 43 (± 2 days)	Day 49-56		
Urinalysis *	X	X	X	X		X	Urine to be checked for protein, glucose, blood, leukocyte esterase, specific gravity and pH. Microscopic examination of sediment if blood, protein, or leukocyte esterase positive on dipstick.
Pregnancy test (WOCBP)	X	X	X	X		X	Serum/urine pregnancy test must be performed (urine pregnancy test: minimum sensitivity 25 IU/L or equivalent units of hCG) within 24 hours prior to administration of study drug. If the pregnancy test is positive, hold all study drugs and perform confirmatory testing. If pregnancy is confirmed, permanently discontinue all study drug and immediately notify Sponsor per Section 6.4 .
Adverse Event Reporting & Concomitant Medication Assessments^d							
Concomitant medication assessments	X	X	X	X	X	X	Review prior to dosing
Monitor for non-serious AEs	X	X	X	X	X	X	Non-serious AEs will be collected starting with the first dose of study medication and through 100 days after discontinuation of dosing.
Monitor for SAEs	X	X	X	X	X	X	All SAEs must be collected from the date of subject’s written consent until 100 days post discontinuation of dosing or subject’s participation in the study if the last scheduled visit occurs at a later time. eSAEs should be approved in in the electronic capture system within 5 business days of entry.
Sample Collection							
PK assessments	See Section 5.5 and Table 5.5.1-1						Performed in all subjects.
Immunogenicity assessments	See Table 5.5.1-1						Performed in all subjects.

Table 5.1-2: On-Treatment Procedural Outline

Procedure	Cycles 1 -13					EOT ^{a,b}	Notes
	Day 1 (± 2 days)	Day 15 (± 2 days)	Day 29 (± 2 days)	Day 43 (± 2 days)	Day 49-56		
Efficacy Assessments							
Tumor/Response assessment					X	X	By methods used at baseline. Same modality/scanner should be used for all assessments. Assessed by RECIST v1.1 (Appendix 3). Assessment must be performed prior to initiating the next cycle of treatment.
Brain imaging					X		As clinically indicated.
Bone scan					X		As clinically indicated.

Table 5.1-2: On-Treatment Procedural Outline

Procedure	Cycles 1 -13					EOT ^{a,b}	Notes

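### Section 6.4 lets a pregnant subject stay on study drug, contradicting Section 1.6 for nivolumab (Parts B, D and E) and Table 5.1-2 (all parts)

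*Combined protocol and SAP*

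**What the plan says.** Two places leave room for dosing to continue in a pregnant subject.

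- Section 6.4 makes discontinuation the usual course rather than the universal one. It adds that, if benefit is thought to outweigh risk and after consultation with the sponsor, "the pregnant subject may continue study drug after a thorough discussion of benefits and risk with the subject".
- Section 3.11, in the paragraph on pregnancy after the discontinuation list, also describes discontinuation as the usual course. It then says: "If the Investigator determines a possible favorable benefit/risk ratio that warrants continuation of study drug", a discussion with the Medical Monitor or designee must take place.

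Two places close that room.

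- Section 1.6 reports pregnancy losses and infant deaths in monkeys exposed to nivolumab, and says that these findings "suggest a potential risk to human pregnancy if there is continued treatment with nivolumab during pregnancy". It then states that "nivolumab exposure during human pregnancy has not been permitted in clinical trials, and is not permitted in this protocol".
- The pregnancy-test note in Table 5.1-2 tells sites to hold all study drugs on a positive test and run a confirmatory test. It continues: "If pregnancy is confirmed, permanently discontinue all study drug and immediately notify Sponsor", with a reference to Section 6.4 for the notification.

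On scope, Section 4 says: "All protocol-specified investigational and non-IPs are considered study drug". Section 4.1.1 names both BMS-986156 and nivolumab as investigational products.

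**The concern.** The investigator reading the schedule of procedures at a dosing visit and the investigator reading Section 6.4 get different instructions on a fetal-safety decision. An investigator and the sponsor could agree to continue under Section 6.4, believe that they are following the protocol, and still breach Table 5.1-2 in any part and Section 1.6 in the nivolumab parts. The hazard that Section 1.6 names is continued nivolumab treatment during pregnancy, which is what Section 6.4 allows. At stake are subject and fetal safety and whether the protocol can be followed consistently. No estimate or error rate is affected.

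**Working it through.** No arithmetic applies, since the point concerns conflicting instructions. The check sets the current operative text side by side.

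| Place | Instruction on pregnancy | Drug covered | Parts covered |
|---|---|---|---|
| Section 6.4 | May continue in a rare case, after sponsor consultation and discussion with the subject | Study drug (both agents) | A to E |
| Section 3.11, pregnancy paragraph | Contemplates continuation; Medical Monitor discussion required | Study drug (both agents) | A to E |
| Section 1.6 | Exposure not permitted | Nivolumab | B, D, E |
| Table 5.1-2 note | Permanent discontinuation once confirmed, no exception stated | All study drug | A to E |

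**Step 1: does the Section 6.4 permission reach nivolumab?** Yes. Sections 4 and 4.1.1 make both agents study drug, and Section 6.4 does not restrict the term. Nivolumab is given in Parts B, D and E, so Section 6.4 conflicts with Section 1.6 in 3 of 5 parts.

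**Step 2: is Section 1.6 only about eligibility at entry?** No. Its concern is continued treatment during pregnancy, and its ban is on exposure. A subject who conceives on treatment and goes on receiving nivolumab falls within it.

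**Step 3: does the Section 6.4 reference in Table 5.1-2 import the exception?** Not as written. The reference is attached to notifying the sponsor, and the order to discontinue stands without a condition. The table therefore conflicts with Section 6.4 in 5 of 5 parts. Even if the exception were imported, the contradiction with Section 1.6 would remain.

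**Step 4: how far does Section 3.11 go?** Section 6.4 says outright that the subject may continue. Section 3.11 requires a discussion if continuation is being considered, so it permits continuation in effect but not in so many words.

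**Step 5: can a site comply with everything?** Yes, by always discontinuing. The defect is confined to the route that Section 6.4 opens and Section 3.11 supports.

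**Step 6: how often could this arise?** The documents do not give the number of women of childbearing potential, so no count is offered. Several safeguards make cases rare. Section 3.9.1 requires a negative test within 24 hours before study drug starts. It also requires two contraceptive methods, although complete abstinence alone is accepted and women continuously not heterosexually active are exempt. Table 5.1-2 repeats testing before dosing. Against that, cohorts 2, 4 and 9 enrol cervical cancer and cohort 7 ovarian cancer, and treatment in Parts D and E can run to 3 + 3 + 7 = 13 cycles of 8 weeks (13 × 8 = 104 weeks).

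**The case against.** The best reply is that the protocol has one coherent scheme: a default of stopping and a rare exception. On this view, Section 6.4 holds the detailed rule, Table 5.1-2 is a summary that points to it, and Section 1.6 is background. All study drug is held on a positive test, and continuation needs sponsor consultation and a discussion with the subject, so no site can continue alone.

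The safeguards are real and limit how often the exception could be used. They do not reconcile the text. Section 1.6 speaks of what this protocol permits, and the table's order carries no exception. Section 6.4 also does not look tailored to this trial: it mentions tapering the dose, whereas Section 4.3.3 bars dose reduction within a subject for either drug.

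Two parts of the defence stand, and each blocks a stronger reading.

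- A reader might infer that Section 3.11 contradicts itself, because pregnancy is on the list introduced by "Subjects MUST discontinue investigational product (IP) (and non-IP at the discretion of the Investigator) for any of the following reasons" and that bullet has no exception, while the progression bullet has one ("unless subject meets criteria for treatment beyond progression"). That does not follow. The later paragraph deals specifically with pregnancy and is naturally read as qualifying the bullet, so the bullet is not counted here as a separate conflict.
- A reader might infer that Section 1.6 forbids BMS-986156 in pregnancy too. Its ban and its animal findings concern nivolumab only. For the monotherapy parts, choosing between an absolute rule and a rare exception is a policy decision for the sponsor. The requirement there is only that Section 6.4 and Table 5.1-2 agree.

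**Conclusion.** The contradiction is real. Section 6.4 permits, and Section 3.11 contemplates, a continuation that Section 1.6 forbids for nivolumab in Parts B, D and E and that Table 5.1-2 forbids for all study drug in Parts A to E. This rests on reading study drug as Section 4 defines it and on taking the table's reference to Section 6.4 as governing notification only. If the reference is read more broadly, the conflict with the table weakens but the conflict with Section 1.6 is untouched.

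The change should be made: probability is low, the consequence in a single case could be severe, and the correction is cheap. The documents do not support inferring an expected number of exposed pregnancies, or that a site could continue dosing without the sponsor's involvement.

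**What to change.** In Sections 6.4 and 3.11, delete the sentences that make discontinuation apply only in most cases, and delete the text on continuing. Replace both with: *If pregnancy is confirmed, all study drug is permanently discontinued.* Keep the text on immediate notification, the Pregnancy Surveillance Form and follow-up.

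Section 1.6 requires this for Parts B, D and E. For Parts A and C, adopting the rule already in Table 5.1-2 is simplest. If the sponsor prefers to keep the exception there, Sections 6.4 and 3.11 must limit it expressly to Parts A and C, and the Table 5.1-2 note must state it. Adding a general exception to the table alone is not enough, because Section 1.6 would still be contradicted in the nivolumab parts. Nor is removing the exception only in Parts B, D and E, because Section 6.4 and the table would still disagree in Parts A and C.

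The cost is wording in two sections, plus the table note if the exception survives in Parts A and C, made through a protocol revision under Section 9.1.1. The downside is losing the rare sponsor-approved exception, either entirely or in the nivolumab parts only.

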6.5 Overdose

An overdose is defined as the accidental or intentional administration of any dose of a product that is considered both excessive and medically important. All occurrences of overdose must be reported as an SAE (see [Section 6.1.1](#) for reporting details).

6.6 Potential Drug Induced Liver Injury (pDILI)

Wherever possible, timely confirmation of initial liver-related laboratory abnormalities should occur prior to the reporting of a pDILI event. All occurrences of pDILIs, meeting the defined criteria, must be reported as SAEs (see [Section 6.1.1](#) for reporting details).

Potential drug induced liver injury is defined as:

- 1) Aminotransferase (ALT or AST) elevation > 3 times ULN,
- 2) Total bilirubin > 2 times ULN, without initial findings of cholestasis (elevated serum ALP),
AND

- 3) No other immediately apparent possible causes of AT elevation and hyperbilirubinemia, including, but not limited to, viral hepatitis, preexisting chronic or acute liver disease, or the administration of other drug(s) known to be hepatotoxic.

6.7 Other Safety Considerations

Any significant worsening noted during interim or final PEs, ECG, x-ray filming, and any other potential safety assessment required or not required by protocol should also be recorded as a nonserious or serious AE, as appropriate, and reported accordingly.

7 DATA MONITORING COMMITTEE AND OTHER EXTERNAL COMMITTEES

Not applicable.

8 STATISTICAL CONSIDERATIONS

8.1 Sample Size Determination

8.1.1 Dose Escalation

As a Phase 1 dose-escalation trial, the sample size at each dose in these arms depends on observed toxicity and posterior inference. Approximately 60 subjects are expected to be treated during the dose-escalation phase (around 30 subjects for BMS-986156 monotherapy and around 30 subjects for BMS-986156 in combination with nivolumab). Initially approximately 3 subjects will be treated at the starting dose levels of BMS-986156 or BMS-986156 in combination with nivolumab. Additional subjects will be treated in recommended dose levels per BLRM (-Copula) during the dose-escalation phase. At most 12 DLT-evaluable subjects will be treated at each dose level.

Additional subjects may be treated at any dose level at or below the MTD or MAD (if no MTD is identified) for further evaluation of safety, [REDACTED] PK parameters as required. At most 12 DLT-evaluable subjects will be treated at each dose level.

8.1.2 Cohort Expansion

Part C contains 2 cohorts of 25 subjects each in monotherapy cohort expansion,. Each cohort in the combination cohort expansion phase (parts D and E) will contain approximately 40 subjects. Forty subjects in parts D and E are planned with the goal of achieving a width of approximately 20% in the 95% confidence interval for ORR, and to provide additional information on safety. Patients in any cohort who discontinue for reasons other than disease progression, death, or treatment-related toxicity may be replaced.

For initial safety evaluation of 480 mg BMS-986156/480 mg nivolumab Q4W in Part E, 6 subjects will be enrolled and followed for a minimum of 2 weeks (please refer to [Section 3.6](#) for the rationale for 2 week period) prior to opening Part E to full enrollment.

If in a cohort of 40 subjects, 10 or 15 responses are observed, then the lower limit of the one-sided 90% CI for the ORR would be 16%, and 27% respectively. These calculations are made using the Clopper-Pearson method for exact confidence intervals. If the true ORR in a tumor type is 40%, then with 40 subjects there is 93% chance of observing at least 12 responses, and 87% chance of observing at least 13 responses, and there is 7% chance of observing 11 or fewer responses.

Continuous interim evaluations and monitoring of safety and efficacy based on the totality of data will be carried out throughout the expansion phase. Decisions regarding continuing enrollment based on these evaluations will be made through discussion between the Sponsor and investigators based on totality of data and overall clinical activity (such as but not limited to duration of response, quality of response, clinical assessment of response and/or SD and safety). The number of subjects receiving treatment of the planned sample size is approximate and may exceed the specified numbers due to unknown time to response and true recruitment rate (i.e additional participants may be enrolled to compensate the 25%-35% of the screening failure rate in combination with the non response evaluable rate to account for participants who may drop out of the study without being evaluable for response and/or true recruitment rate is much higher than anticipated and thus, Sponsor will examine on the totality of data to determine the benefit/risk ratio as well as overall clinical activity when making the final Go/no Go decision.

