8.3.2.2 Efficacy

The second antitumor activity of BMS-986156 alone and BMS-986156 in combination with nivolumab will be measured by ORR and duration of response based on RECIST 1.1. Disease assessment with CT and/or MRI as appropriate will be performed at baseline and every 8 weeks during Treatment Phase until disease progression per RECIST v1.1, or until confirmed disease progression for subjects treated beyond progression [defined as an additional 10% or greater increase in tumor burden volume from time of initial progression (including all target lesions and new measurable lesions)], discontinuation of treatment or withdrawal from study. Subjects having received local palliative therapy will be documented as having had disease progression for the purpose of efficacy analyses.

- Best overall response (BOR): defined as the best response designation over the study as a whole, recorded between the dates of first dose until the last tumor assessment prior to subsequent therapy. BOR is assessed by investigator (BIRC) per RECIST 1.1 criteria.
- ORR is defined as the proportion of all treated subjects whose BOR is either a CR or PR.
- Duration of response, computed for all treated subjects with a BOR of CR or PR, is defined as the time between the date of first response and the date of disease progression or death, whichever occurs first.
- PFSR at 24 *Weeks*: The proportion of treated subjects remaining progression free and surviving at 24 *weeks*. The proportion will be calculated by the K-M estimate which takes into account censored data.

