8.4.3 Efficacy Analyses

Listing of tumor measurements will be provided by subject and study day in each arm and dose level. Individual subject's BOR will be listed based on RECIST 1.1.

To describe the antitumor activity of BMS-986156 alone or in combination with nivolumab, ORR will be calculated. ORR and corresponding 2-sided exact 95% exact CI by the Clopper and Pearson method will be provided by treatment and dose level. Median duration of response and corresponding two-sided 95% CI will be reported by treatment and dose level. Duration of response will be analyzed using the Kaplan-Meier method.

In addition, PFSR, the probability of a subject remaining progression free or surviving to 24 weeks, will be estimated by the Kaplan-Meier methodology, by treatment and dose level. The corresponding 90% CI will be derived based on Greenwood formula. PFSR at month 12 will be estimated using the same method for the combination treatment BMS-986156 and nivolumab.

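### Forty subjects per cohort do not give a 95% CI for ORR about 20 points wide at the response rates Section 8.1.2 discusses; the planned exact interval is about 28 to 32 points wide.

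*Combined protocol and SAP*

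**What the plan says.** Section 8.1.2 sets the size of the combination expansion cohorts: "Each cohort in the combination cohort expansion phase (parts D and E) will contain approximately 40 subjects". The next sentence gives the reason for forty, "with the goal of achieving a width of approximately 20% in the 95% confidence interval for ORR", together with further safety information. No response rate is attached to the width.

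The section then illustrates what 40 subjects provide: "10 or 15 responses are observed, then the lower limit of the one-sided 90% CI for the ORR would be 16%, and 27% respectively". It names the method: "These calculations are made using the Clopper-Pearson method for exact confidence intervals". It continues: "If the true ORR in a tumor type is 40%, then with 40 subjects there is 93% chance of observing at least 12 responses", followed by the probabilities for at least 13 responses (87%) and for 11 or fewer (7%).

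Section 8.4.3 fixes the interval to be reported: "ORR and corresponding 2-sided exact 95% exact CI by the Clopper and Pearson method will be provided by treatment and dose level". Section 8.3.2.2 fixes the denominator: "ORR is defined as the proportion of all treated subjects whose BOR is either a CR or PR". The synopsis repeats the illustrations but not the width goal.

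**The concern.** At a fixed sample size the width of a binomial interval depends on the response rate, so a width without a rate cannot be checked as it stands. The only rates the section discusses lie between 25% (10/40) and 40% (the assumed true ORR). At those rates an interval from 40 subjects is well over 20 points wide.

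The width is the only target for interval width given for the Part D and E cohort size. The same section leaves continuation of enrolment and the go/no-go decision to the totality of data, including overall clinical activity. A reader who relies on the sentence would expect an interval about two-thirds as wide as a cohort with an ORR of 25% to 40% will give.

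**Working it through.** **Inputs**
- n = 40 per cohort (8.1.2).
- Two-sided 95% Clopper-Pearson interval (8.4.3).
- Observed responses x = 10 and 15, cut points of 11, 12 and 13, and a true ORR of 40% (8.1.2). I add x = 16, which is 40% of 40.
- Assumption: the width applies to one cohort of 40.

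**1. The section's other figures**

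The one-sided 90% lower limit is the 0.10 quantile of Beta(x, n − x + 1):
- x = 10: Beta(10, 31) gives 16.15% (stated 16%).
- x = 15: Beta(15, 26) gives 27.14% (stated 27%).

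With X ~ Binomial(40, 0.40):
- P(X ≥ 12) = 92.9% (stated 93%).
- P(X ≥ 13) = 87.1% (stated 87%).
- P(X ≤ 11) = 7.1% (stated 7%).

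All of these reproduce.

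**2. Width of the planned interval**

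Lower limit = 0.025 quantile of Beta(x, n − x + 1). Upper limit = 0.975 quantile of Beta(x + 1, n − x). Width = upper − lower.

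| Responses | ORR | Exact 95% CI | Width (points) |
|---|---|---|---|
| 3/40 | 7.5% | 1.6% to 20.4% | 18.8 |
| 4/40 | 10% | 2.8% to 23.7% | 20.9 |
| 5/40 | 12.5% | 4.2% to 26.8% | 22.6 |
| 8/40 | 20% | 9.1% to 35.6% | 26.6 |
| 10/40 | 25% | 12.7% to 41.2% | 28.5 |
| 11/40 | 27.5% | 14.6% to 43.9% | 29.3 |
| 12/40 | 30% | 16.6% to 46.5% | 30.0 |
| 13/40 | 32.5% | 18.6% to 49.1% | 30.6 |
| 15/40 | 37.5% | 22.7% to 54.2% | 31.5 |
| 16/40 | 40% | 24.9% to 56.7% | 31.8 |

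The stated 20 points falls between 3/40 and 4/40. Relative to the actual width it is 20/28.5 = 0.70 at 10/40 and 20/31.8 = 0.63 at 16/40.

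**3. Averaged over the outcomes a cohort might produce**

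Expected width = Σ P(X = x) × width(x), with X ~ Binomial(40, p). The last column is the probability that the width is 21 points or less, which in practice means 4 or fewer responses.

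| True ORR | Expected width (points) | P(width ≤ 21) |
|---|---|---|
| 10% | 20.3 | 63% |
| 20% | 26.1 | 7.6% |
| 25% | 28.1 | 1.6% |
| 40% | 31.4 | under 0.01% |

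**4. Other readings of the figure**
- *Another interval method.* The Wald width is 2 × 1.96 × √(p(1 − p)/40). At p = 0.25 this is 3.92 × √(0.1875/40) = 26.8 points; at p = 0.40 it is 30.4. Wilson gives 26.0 and 29.1.
- *Half-width.* Half the exact width is about 14 points at 10/40 and about 16 at 16/40, so 20 does not match that either.
- *Another confidence level.* A two-sided 80% exact interval is 19.7 points wide at 10/40 and 21.9 at 16/40.
- *Pooling by treatment and dose level.* Part E has 2 × 40 = 80 subjects: 19.9 points at 20/80 and 22.4 at 32/80. Part D has 6 × 40 = 240: 11.3 at 60/240 and 12.7 at 96/240. Neither is an interval from forty subjects.

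**5. Sample size that would give 20 points**

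An exact width of 20 points or less needs about 80 subjects at an ORR of 25%, 98 at 37.5% and 100 at 40%.

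**The case against.** The sentence states a goal and an approximate figure, and the figure is attainable: at a true ORR of 10% the expected width is 20.3 points. The documents give no expected ORR by tumour type, and Section 3.5 refers to heterogeneous response rates in the mixed cohort. On this view 25% to 40% are illustrations, not planning assumptions, and the defect is an unstated rate, not a failed calculation. This stands in part. The 20% figure is not impossible, and the two-thirds comparison applies only at about 25% to 40%. But the text names no low rate, and every illustration in the section is at 25% or above.

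Section 8.4.3 reports the interval by treatment and dose level and does not name cohorts, so the per-cohort reading is an assumption. It is a well-supported one: the sentence before the width sets the size of each cohort, and the probability statement refers to 40 subjects in a tumour type.

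The figure may come from a mislabelled confidence level. The two-sided 80% interval is the counterpart of the one-sided 90% limits in the same section, and it is close to 20 points wide across the illustrated range. The documents neither confirm nor exclude this. If it is the source, the stated 95% width is still wrong at those rates.

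Finally, little depends on the width. The synopsis describes the expansion sample sizes as guidance, and the safety aim, the one-sided limits and the probabilities also support n = 40. That is fair, and it limits the weight of the point.

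**Conclusion.** The concern holds. Read per cohort of 40, the 95% width of about 20% is reached only at an ORR of about 10% or lower. Over the section's own range of 25% to 40% the planned exact interval is 28.5 to 31.8 points wide (expected width 28.1 to 31.4), about 8 to 12 points more than stated.

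The conclusion rests on the per-cohort reading and on taking the section's illustrations as the rates of interest. It does not depend on the choice among the exact, Wald and Wilson methods.

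The sentence should be corrected because it is a stated reason for the sample size, but the consequence is small. ORR is secondary, Section 1.3 says no hypotheses are formally evaluated, no decision rule uses the width, and the intervals in the final report will be correct whatever this sentence says.

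**What to change.** Keep n = 40 and restate the width sentence in Section 8.1.2, for example: *With 40 subjects in a cohort, the exact two-sided 95% CI for ORR has a width of approximately 27% to 32% for observed ORRs of 20% to 40%.* This matches 26.6 points at 8/40 and 31.8 at 16/40.

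Alternatively, keep a figure near 20% and name its rate: *approximately 21% at an observed ORR of 10%*. Before choosing, the sponsor should check whether the original figure was computed at a level other than 95%.

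The one-sided 90% limits and the 93%, 87% and 7% probabilities can stay. The synopsis does not carry the width statement and needs no change.

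The cost is one sentence and a less favourable stated precision. No subjects are added and no analysis changes.
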